Yield of Diagnostic Tests and Management of Crofelemer for Chronic Idiopathic Diarrhea In Non-HIV Patients: A Pilot Study

NCT03898856

Version Date: 12/06/2023

Yield of Diagnostic Tests and Management of Crofelemer for Chronic Idiopathic Diarrhea In Non-HIV Patients: A Pilot Study

Principal Investigator

[name]

Chief - Division of Gastroenterology, Hepatology and Nutrition

Sterling Professor of Medicine

University of Texas Health Science Center at Houston

Co-Director, Ertan Digestive Disease Center

[REDACTED]

[REDACTED]

[REDACTED]

[REDACTED]

[REDACTED]

[REDACTED]

Co-Investigator

[name]

PGY-2 (Second Year Resident)

Department of Internal Medicine/Pediatrics

University of Texas Health Science Center at Houston

[REDACTED]

[REDACTED]

Co-Investigator

[name]

PGY-5 (Clinical Fellow)

Division of Gastroenterology, Hepatology and Nutrition

University of Texas Health Science Center at Houston

[REDACTED]

[REDACTED]

Collaborators/ Sponsors

1. Napo Pharmaceuticals

[REDACTED]

San Francisco, CA 94105

[REDACTED]

[REDACTED]

Study Coordinator

[name], MBA

Sr. Clinical Trial Program Manager

Department of Internal Medicine

[REDACTED]

[REDACTED]

[REDACTED]

[REDACTED]

Principal Clinical Site

Ertan Digestive Disease Center (EDDC)

University of Texas Health Science Center at Houston (UTHealth)/ Memorial Hermann Healthcare System (MHHS)

[REDACTED]

[REDACTED]

[REDACTED]

Study Population

Males and females between age 18-75 years with chronic functional diarrhea (defined as 3 non-bloody loose stools per day or more than 20 non-bloody loose stools per week for \geq 4 weeks) without an obvious cause after evaluation for organic causes presenting to Ertan Digestive Diseases Center (EDDC) in Houston.

Sample Size

Up to 100 Subjects

Study Duration

Approximately one year from institutional review board (IRB) approval

Subject Duration

Approximately 3 to 4 months per subject

Tentative Dates of Study

Estimated commencement date of the study: Nov 2019

Estimated completion date of the study: May 2021

Type of Study

Pilot Study; Non-Blinded Clinical Trial

Amount of Product Required

2 tablets x 28 days x 25 patients = 1,400 crofelemer tablets

No placebo needed. The drug will be used solely to conduct the study and all safety and regulatory reporting obligations will be followed. Any unused drug will be returned to Napo Pharmaceuticals within 90 days of study completion.

Background and Rationale

Chronic Diarrhea and Epidemiology

Chronic diarrhea is a common complaint of patients presenting to family practitioners, internists and is one of the most common reasons for referral to gastroenterologists. It is estimated that the prevalence of chronic idiopathic diarrhea in developed countries (including the US) is approximately 3-5% [1-3]. It has a significant negative effect on health-related quality of life (HRQOL) and causes high economic burden on patients and society. The American Gastrointestinal Association Burden of Illness study showed that the estimated annual direct and indirect costs associated with chronic diarrhea is up to \$524 million per year and \$136 million per year, respectively [3].

Diagnostic Evaluation of Chronic Diarrhea

There are many causes of chronic diarrhea known to man and several algorithms have been created for the evaluation chronic diarrhea [2-4]. Over the last 10 years, additional diagnostic tools have become available that may increase the identification of heretofore unappreciated causes of chronic diarrhea. In addition to traditional stool analyses and lower gastrointestinal endoscopy, breath testing for specific carbohydrate maldigestion, stool multiplex examinations for gastrointestinal infection, and assays for carbohydrate and bile acid malabsorption have become available in routine clinical practice. As a consequence, clinical awareness of the conditions diagnosed by these emerging assays has increased, but prevalence values for these conditions and the relative importance of their contributions to the symptoms of chronic diarrhea remain unknown. For instance, recent estimates have placed the prevalence of bile acid malabsorption (BAM) in patients with irritable bowel syndrome (IBS) with diarrhea between 25-50%. Up until recently, there has been no diagnostic test available outside research institutions for BAM and treatment for this condition has been empiric bile acid sequestrant therapy, which can interfere with the absorption of other medications. The availability of the serum 7C4 test for BAM may be an important development in the management of patients with chronic diarrhea, but outcomes data are lacking.

Congenital sucrase-isomaltase enzyme deficiency (CSID) is an often unrecognized, autosomal recessive disorder with wide phenotypic heterogeneity with symptoms such as chronic diarrhea, bloating, abdominal pain, and flatulence that are non-specific and commonly associated with other digestive disorders. This results from maldigestion of sucrose and starches in the diet, release of water secondary to high intraluminal osmolality, and subsequent bacterial fermentation [5]. Recent work has shed some light on the hypothesis that CSID may be more prevalent than we previously believed with estimates ranging from 9.3% to 21% [6,7]. Demonstration of normal

duodenal or jejunal mucosal histology and low to absent sucrase activity detected by enzyme assay remains the gold standard for diagnosis of CSID [8-11]. An evolution of the H₂ BT introduced in the early 1970's was the measurement of isotope-labeled CO₂ in breath using ¹³C or ¹⁴C [12]. These tests depend on measurement of changes in isotope labeled breath via infrared mass-dispersion spectrophotometry which is simple and has a short turnaround time [13-15]. Since the introduction of mass spectrometers for the detection of the stable isotope of ¹³C in expired air the BT technique has been adapted for the study of malabsorption with collection systems that are well tolerated and widely reproducible. ¹³C Breath testing is a non-invasive, 90-minute test that can be easily administered by the patient at home. An 8 hour fast is required after which the patient collects a baseline sample and then 20 gram of ¹³C Sucrose is administered orally. The patient collects breath samples 30 minutes apart by blowing through a straw into labeled, screw-cap glass tubes. These tubes are then mailed to the analyzing lab and results are obtained within 24 hours.

Management of Chronic Diarrhea

Despite the advances in the medical field, in a substantial number of cases, no organic or functional etiology can be determined. In those circumstances and in cases where no specific treatment is available or specific treatment fails to affect the cure, symptomatic treatment of diarrhea remains the mainstay of management. Variable success has been seen with pharmacological agents including anti-secretory (octreotide), anti-motility (loperamide and diphenoxylate atropine), and adsorbent medications along with adjunctive non-pharmacologic measures such as dietary modifications (fiber supplements like psyllium or absorbents like kaolin) [2].

About Crofelemer

Crofelemer is a novel compound isolated from the plant *Croton lechleri* (family *Euphorbiaceae*) found in the western Amazonian regions of South America. (Attachment 6) This naturally occurring extract is an acid-labile, proanthocyanidin oligomer found in the red latex of the plant [16]. Native populations of South America have used the sap of the plant for self-treatment of chronic diarrhea for many years. Crofelemer is primarily composed of (+)-catechin, (-)-epicatechin, (+)-gallocatechin, and (-)-epigallocatechin monomer units linked in random sequence (Figure 1).

The mechanism of action of crofelemer is through dual inhibition cyclic adenosine monophosphate (cAMP)-stimulated cystic fibrosis transmembrane conductance regulator (CFTR) chloride ion (Cl) channel, and the calcium-activated Cl channels (CaCC) at the luminal membrane of enterocytes [17,18]. This structurally unrelated inhibition

of intestinal chloride channels normalizes the flow of Cl and water in the GI tract, leading to anti-secretory effects of crofelemer. Systemic absorption is minimal and concentrations of crofelemer in plasma remained below the level of quantitation (50 ng/mL) in studies. There are no active metabolites identified and the route of elimination is unknown.

Previously, crofelemer has been investigated for the treatment of several types of chronic diarrhea, including traveler's diarrhea [19], AIDS-associated diarrhea [20], and infectious diarrhea such as cholera [21]. Crofelemer has also been studied in patients with diarrhea-predominant IBS (IBS-D) [22]. Crofelemer has also been evaluated as a topical application in patients with AIDS for the treatment of recurrent genital and perianal herpes lesions.

Due to its large chemical structure, crofelemer has minimal systemic absorption when given orally, irrespective of concomitant food intake or duration of exposure. It has demonstrated a good safety profile and is well tolerated in current published studies [23]. In a study performed in 2002 on 184 travelers returning from Mexico, Jamaica, and the United States-Mexico border, De Cesare et al. demonstrated a 21% reduction in the duration of traveler's diarrhea in more than 90% of the individuals with crofelemer [19]. Holodniy et. al conducted a multicenter, phase II, randomized, double blind, placebo-controlled study [20]. 26 patients with AIDS received a 4-day course of crofelemer with marked reduction in stool frequency and stool weight compared to placebo. Crofelemer has also been efficacious in reducing pain and discomfort in female patients with IBS-D. This was shown by Mangel et al. in a placebo-controlled trial in 2008 [22]. The phase 3 ADVENT trial lead by McArthur et al. used a 2-stage design [23]. The first stage included a placebo-controlled phase with approximately 200 HIV-seropositive patients on HAART therapy, randomized to receive crofelemer 125 mg, 250 mg, or 500 mg or placebo twice daily. After a responsiveness analysis, crofelemer 125mg twice daily was used in a placebo controlled second stage trial. Clinical response was defined as ≤ 2 watery stools per week during ≥ 2 of the 4 weeks of the placebo-controlled phase. Crofelemer provided a 17.6% response rate compared to only 8.0% in the placebo group. It decreased the number of daily watery bowel movements and daily stool consistency score, but was ineffective in controlling urgency, abdominal pain, and incontinence. Both clinical trial stages were followed by 20-week open label trial with weekly response-assessment. In this trial the placebo-response rate rose for weekly responders to 56%. More pronounced crofelemer treatment effects were observed in patients with diarrhea of greater severity (≥ 2 watery stools per day) or duration (> 2 years) or who had used multiple (≥ 2) antidiarrheal medications prior to the study.

Formerly known as Fulyzaq, crofelemer was approved by US-FDA in December 2012 for symptomatic treatment of HIV-related diarrhea in the dose of 125mg tablets taken two times a day [24]. It was the first botanical therapy to receive FDA approval and is now marketed under the name of Mytesi®. The most common adverse reactions for crofelemer that occurred in at least 2% of patients in the ADVENT trial at a higher incidence than placebo were upper respiratory tract infection, bronchitis, dry cough, flatulence and increased bilirubin [23](Table 1). Adverse reactions that occurred in between 1% and 2% of patients taking a 250 mg daily dose of crofelemer were abdominal pain, acne, increased aspartate aminotransferase, increased conjugated bilirubin, increased unconjugated blood bilirubin, constipation, depression, dermatitis, dizziness, dry mouth, dyspepsia, gastroenteritis, herpes zoster, nephrolithiasis, pain in extremity, pollakiuria, procedural pain, seasonal allergy, sinusitis and decreased white blood cell count.

There are no absolute contraindications reported for crofelemer use. It is a white, oval, enteric-coated 125 mg delayed-release tablet. The inactive ingredients of crofelemer are - microcrystalline cellulose, croscarmellose sodium, colloidal silicon dioxide, and magnesium stearate. The coating ingredients are - ethylacrylate and methylacrylate copolymer dispersion, talc, triethyl citrate, and white dispersion, which contains xanthan gum, titanium dioxide, propyl paraben, and methyl paraben. Since there is no known relation between food intake and drug administration, crofelemer can be taken with or without meal. However, it should not be crushed or chewed and is intended to be swallowed whole. It is marketed as a bottle of 60 tablets and should be stored at 20°C-25°C (68°F-77°F); excursions are permitted between 15°C-30°C (59°F-86°F) (Attachment 6 and 7).

With the increasing interest in discovering uses of crofelemer in other spectrum of diarrheal disease, objective of this study will be to evaluate the efficacy of crofelemer in non-HIV patients with chronic idiopathic diarrhea. With most patients relying on anti-motility agents or other adjunct therapies with variable success, there is a promise in crofelemer for future studies.

Chronic Diarrhea and Health-Related Quality of Life

Chronic diarrhea can result in a decline in nutritional status and subsequent decline in functional status and overall quality of life. HRQOL is a multidimensional construct that consists of three broad domains – physical, psychological, and social functioning – that are affected by one's disease and/or treatment [25]. The measures of

quality of life may be influenced by factors unrelated to the health status of the patient including change in their expectations and aspirations as circumstances change, values patients place on life, their risk aversion, or their attitude towards certain type of medical intervention [26]. Understanding how chronic diarrhea affects HRQOL is still very limited and restricted to specific population studies largely focusing on people living with AIDS and IBS [27-29]. There is no HRQOL questionnaire specifically developed, or validated for, chronic idiopathic diarrhea. Short-Form 36 (SF-36) is a generic questionnaire developed in the early 1990's to evaluate HRQOL in illness and make comparisons with the background population or between different diseases. It is a self-administered, general questionnaire comprising 36 items, which is well validated and accepted. Thirty-five of the items are grouped into eight scales: physical function (PF), role limitations due to physical disability (RP), bodily pain (BP), general health perception (GH), vitality (VT), social function (SF), role limitation due to emotional problems (RE), and mental health (MH). The results are presented as scale scores ranging from 0 (worst possible health state) to 100 (best possible health state) following the standard SF-36 scoring algorithm [30-32]. With our study, we aim to shed some light on the perception of health and quality of life in patients with chronic idiopathic diarrhea. In addition, we will also look at any change in that perception after administration of crofelemer for 4 weeks.

Objectives

Primary Objective – Assess the efficacy of crofelemer in adult, non-HIV patients with idiopathic chronic diarrhea

Secondary Objectives -

1. Determine the prevalence of identifiable causes of chronic diarrhea in a non-HIV patients
2. Assess the diagnostic yield, in terms of identification of treatable etiologies, of commercially available diagnostic evaluations in adult, non-HIV patients with chronic idiopathic diarrhea; i.e., evaluate which tests, among the standard diagnostic tests commonly conducted as part of the evaluation of chronic idiopathic diarrhea, are most likely to identify a treatable cause of the diarrhea.
3. Assess the usefulness of CSID testing in adults with chronic idiopathic diarrhea via sucrase enzyme level testing on small intestinal biopsies, and ¹³C-SBT.
4. Analyze the relationship between chronic idiopathic diarrhea and health-related quality of life and assess the impact of crofelemer treatment on health-related quality of life

Details of the Study

Definition of Chronic Diarrhea - Persistent increase in bowel movement frequency (≥ 3 bowel movements per day or ≥ 20 bowel movements per week) **AND** decrease in consistency of $>50\%$ stools (liquid or watery-Bristol Stool Form Scale type 6 or 7) for more than 4 weeks [33].

Outcome measures

Primary Response to crofelemer- A 50% decrease in mean stool count per week by the end of week 4

Secondary Responses to crofelemer- An improvement (decrease) in stool consistency by more than 2 levels in the Bristol stool scale (Figure 2) [34,35].

2. Changes in HRQOL at T0 and at T+4 weeks

3. Descriptive analysis of the frequency of identified etiologies of chronic diarrhea and the frequency of abnormal diagnostic test results leading to the identification of those etiologies

Treatment Failure/Non-responder -

1. Failure to meet the primary response definition
2. Medication non-compliance: Subjects who missed more than a total of four doses over the 4-week course.
3. Subjects who fail to record at least 80% of the daily symptom diary.

Inclusion Criteria

Males and females between age 18-75 years with chronic diarrhea (defined as 3 non-bloody loose stools per day or more than 20 non-bloody loose stools per week for more ≥ 4 weeks) and Bristol Stool Form Scale for stool consistency of 6/7 with $>50\%$ stool without an obvious cause after evaluation for organic etiologies. Patients of all ethnicities will be included in the study.

Exclusion Criteria

Since the study focuses on chronic idiopathic diarrhea, subjects who may have other organic pathologies or comorbidities that may explain the cause of diarrhea will be excluded.

1. Hematochezia (potentially related to an organic cause).
2. Subjects less than 18 years of age more than 75 years of age (safety and effectiveness of crofelemer has not been established in these age groups).
3. Pregnant females (crofelemer is a Category C drug due to lack of well-controlled studies to study its effects in this population).

4. Lactating females (it is unknown if crofelemer is excreted in the human milk and thus may have unknown adverse effects on the nursing infants).
5. HIV positive individuals.
6. Persons within ability to provide consent and understand the study
7. Persons with history of alcohol abuse or binge drinking.
8. Persons with history of surgical bowel resection or bariatric surgery in the past 12 months.
9. Persons who have undergone cholecystectomy (open or laparoscopic) in the past 3 months.
10. Persons receiving antibiotics currently or have received antimicrobials in the past 4 weeks.
11. Persons with end-organ failures including end-stage renal disease, end-stage liver disease, or severe heart failure.
12. Persons with metastatic hematologic and oncologic malignancies.
13. Persons receiving chemo-radiation or immune-modulators for oncologic or rheumatologic conditions.
14. Persons with any other known organic gastrointestinal or non-gastrointestinal disease process in which diarrhea is a recognized clinical feature.
15. Gluten free diet for previous 3 months and refusal to ingest gluten.

Recruitment strategy

1. Prospective recruitment of patients referred to the Gastroenterology division of UTHealth/MHHS for evaluation and management of chronic diarrhea.
2. Furthermore, presentations will be given to faculty members in the Department of Gastroenterology, Hepatology and Nutrition and Internal Medicine at UTHealth/MHHS to discuss the study and facilitate recruitment of subjects.
3. Inclusion of study criteria and description of study procedures on the research page for the UTHealth/MHHS Gastroenterology Division.
4. Poster advertisements at UTHealth/MHHS bulletin boards with contact information.

Phases of the study

1. Screening period of 4-8 weeks for each patient to undergo diagnostic evaluation to determine eligibility to participate in the study
2. Treatment period of 4 weeks for collection of efficacy data on crofelemer

3. Post-Treatment follow-up for drug efficacy, safety assessment, and overall quality of life analysis

Based on estimated prevalence of identifiable causes of chronic diarrhea in approximately 50% of adult patients and an estimated non-eligibility prevalence of up to 75% of prospective patients, to enroll 25 patients who meet the eligibility criteria for the study, we are estimating that approximately 100 patients will be required to undergo evaluation for this pilot study. This will be achieved over a period of 12-18 months starting from Fall 2019.

Since this is a pilot study with limited data available of the effect of the drug on the specified population, a sample size of 25 subjects is considered safe and feasible to inform potential future randomized controlled trials.

Criteria for termination of trial:

1. Severe unanticipated adverse effects of the drug in the participants
2. Inability to enroll stipulated number of participants over the anticipated study time
3. Withdrawal of more than 50% of the selected subjects from the study. Please note that subjects may withdraw voluntarily from the study at any time of the subject duration. He/she will be required to write a written request addressed to the PI, explaining the reason for withdrawal. New subjects will be enrolled to the study after the screening period, if possible during the total study duration.
4. Enrollment of 25 subjects into the treatment phase or 100 patients in the diagnostic phase, whichever occurs first.

Number of visits/encounters

Four clinic visits at EDDC

1. Pre-screening assessment of subjects (4-8 weeks prior to treatment phase)
2. Discussion of the results of diagnostic tests and evaluations; initiation of treatment with crofelemer 125 mg tablets twice daily (BID) (Day 1) (Attachment 7)
3. Mid-study follow-up (Day 14) for symptomatic evaluation of diarrhea and any adverse events
4. Final post-treatment follow-up on Day 29 **OR** the first business day after completion of treatment

PHASE 1: SCREENING PERIOD

A careful, detailed and comprehensive medical, surgical, and social history will be obtained to categorize the diarrhea and rule out obvious organic causes of diarrhea. All of these diagnostic tests are considered standard of care for the evaluation of chronic idiopathic diarrhea.

The order in which these investigations will be performed will be tailored on a case-to-case basis (patient education for each test is added as an attachment and mentioned in parenthesis)–

1. Complete Blood Count (CBC)
2. Comprehensive Metabolic Panel (CMP)
3. HIV Screening – To screen patients for the study as our study focuses on non-HIV patients only (if not done in previous 6 months)
4. Esophagastroduodenoscopy (Attachment 8) and Colonoscopy (Attachment 9)– (performed by PI) with random and (if required by endoscopic findings) targeted biopsies of the UGI (duodenum) and LGI (colon) tract mucosa sent to the department of pathology for analysis as well testing for CSID (duodenal biopsies)
5. Stool multiplex panel for the following gastrointestinal pathogens:

Campylobacter

Cryptosporidium

E. coli O157

Enterotoxigenic E. coli (ETEC)

Shiga Toxin-producing E. coli (STEC)

Giardia lamblia

Norovirus GI/GII

Rotavirus A

Salmonella

Shigella

Adenovirus 40/41

Entamoeba histolytica

Vibrio cholera

Yersinia enterocolitica

Clostridium difficile

6. Urine Pregnancy Test when clinically indicated
7. Thyroid Panel: Thyroid stimulating hormone and free T4

8. Tissue transglutaminase and IgA
9. C-reactive protein
10. Serum 7C4
11. Gastrin Level
12. Calcitonin Level
13. VIP Level
14. Stool osmolality
15. Stool Qualitative Stool Fat
16. Stool Reducing Substances
17. Stool calprotectin
18. Stool elastase
19. Lactulose Hydrogen Breath Test
20. ¹³C-Sucrose Breath Test
21. HRQOL (SF-36) baseline - This is a questionnaire that consists of 36 questions and asks subjects' views about their health. Subjects will fill this form two times during the total duration of study – at the initial visit prior to starting treatment and once at the end at the post-treatment follow-up (Attachment 5a and 5b).

We estimate that it may take from 4 weeks up to 8 weeks to obtain and complete all the above-mentioned tests.

Patients will be updated by a call from the study coordinator to discuss the results and scheduled the pre-treatment clinic visit.

Diagnostic tests will be denoted as normal, abnormal, or unable to be performed (in the event of insufficient sample, non-compliance, or lab error). Descriptive statistics will be used to denote the percentage of patients with any abnormal diagnostic tests and the frequency of abnormal results for each test, relative to other diagnostic tests, will be computed and recorded for the cohort.

In accordance with good clinical and standard practice, abnormal tests will be evaluated and acted upon as indicated. Any diagnosis of a causative medical condition identified as a result of the standardized diagnostic evaluation will be recorded, as will patient response to appropriate therapy for any identified medical conditions, if any.

PHASE 2: TREATMENT PERIOD

Consecutive patients completing the diagnostic phase who are not identified as having a proven etiology of their chronic diarrhea symptoms will be invited to participate in the treatment phase. With the evidence supporting 125 mg BID dosing of crofelemer as the appropriate dose for response as shown by the ADVENT study, we will be administering the same dose of 125 mg tablets taken by mouth twice daily for our subjects.

We will provide the subjects with a total of 56 tablets for the 28-day course. An IND has not been sought for this study because the study meets the exemption criteria as stated in 21 CFR 312.2(b): investigations using a marketed drug or biologic do not require submission of an IND if all six conditions below are met:

1. It is not intended to be reported to FDA in support of a new indication for use or to support any other significant change in the labeling for the drug.
2. It is not intended to support a significant change in the advertising for the product.
3. It does not involve a route of administration or dosage level, use in a subject population, or other factor that significantly increases the risk (or decreases the acceptability of the risk) associated with the use of the drug.
4. It is conducted in compliance with the requirements for Institutional Review Board/Independent Ethics Committee (IRB/IEC) review and informed consent.
5. It is conducted in compliance with the requirements concerning the promotion and sale of drugs.
6. It does not intend to invoke 21 CFR 50.24 (exception from informed consent for emergency research).

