Participants will be provided with the Daily Symptom Diary on their second visit, prior to treatment initiation. It will be a notebook with the above questions printed on each page with a total of 30 entries and 5 extra pages in the back for any other information that the participant may wish to include (Attachment 3). The completeness of entries and pattern of symptoms will be assessed on the subsequent visits on Day 14 and Day 29. All information will then be noted and uploaded to the study database subsequently. Participants will need to have at least 80% completed entries i.e. 22 diary entries throughout the study period. Any missing entry will be considered as no bowel movements for that day. Any subject with insufficient data entry of less than 22 entries will be categorized a non-responder. No patient identifiers will be included in the diary, other than subject number that corresponds to the master study

enrollment log, which will be maintained electronically. Patients will be given sequential study ID numbers (1 up to 100) upon enrollment into the study.

PHASE 3: POST-TREATMENT FOLLOW-UP

A post-treatment follow-up visit would be scheduled with the PI on Day 29 or the first business day after completion of the crofelemer course. The following variables will be obtained and analyzed for the study -

1. Age (in years)
2. Gender (Male/Female/Other)
3. Ethnicity (Caucasian/Hispanic/African American/Native American/Asian/Other)
4. BMI (in kg/m²)
5. Number of weeks/years of diarrhea fulfilling entry criteria
6. Number of stools per day (Day 0)
7. Number of stools per day (Day 14)
8. Number of stools per day (Day 28)
9. Total number of stools per week (Week 1, 2, 3, and 4)
10. Average consistency of stools (Day 0)
11. Average consistency of stools (Day 14)
12. Average consistency of stools (Day 28)
13. Previous use of other anti-diarrheal agents (Yes/No)
14. Average number of anti-diarrheal agents used per week (Day 0)
15. Average number of anti-diarrheal agents used per week (Day 14)
16. Average number of anti-diarrheal agents used per week (Day 28)
17. Abdominal Pain yes or no and scored from 0 to 10 (0-no pain, 10-worst abdominal pain imaginable)
18. Urgency (according to 0-4 VAS scale)
19. Fecal Incontinence (Yes/No)
20. Other comorbid diagnoses
21. Concomitant medications and dosing
22. HRQOL (SF-36) Post-treatment (Attachment 5b)

Data and Safety Monitoring

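### The only pre-treatment SF-36 appears to be taken at the screening visit, so the HRQOL change labelled as four weeks would span 8 to 12 weeks

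*Combined protocol and SAP*

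**What the plan says.** Secondary objective 4 has two halves. One relates chronic idiopathic diarrhea to health-related quality of life. The other is to "assess the impact of crofelemer treatment on health-related quality of life". The background section on HRQOL states the second aim as "any change in that perception after administration of crofelemer for 4 weeks", and Outcome measures lists "Changes in HRQOL at T0 and at T+4 weeks". T0 is not defined in the visible text.

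The SF-36 is scheduled in PHASE 1: SCREENING PERIOD, item 21, which provides for two completions per subject: "at the initial visit prior to starting treatment and once at the end at the post-treatment follow-up". The sentence after that list reads "We estimate that it may take from 4 weeks up to 8 weeks to obtain and complete all the above-mentioned tests".

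Number of visits/encounters sets out four clinic visits. The first is "Pre-screening assessment of subjects (4-8 weeks prior to treatment phase"). The second, on Day 1, covers the test results and the start of crofelemer, and no SF-36 is mentioned there. The third is on Day 14. For the last, PHASE 3 says "A post-treatment follow-up visit would be scheduled with the PI on Day 29 or the first business day after completion of the crofelemer course", and the post-treatment SF-36 is collected then. The Statistics section adds only that HRQOL changes will be described in the usual way.

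**The concern.** A change over four weeks of treatment needs a baseline taken when treatment starts. If the baseline form is completed at visit 1, the change also includes the whole diagnostic work-up, during which no crofelemer is given. In those weeks patients undergo endoscopy and extensive testing, and abnormal findings are acted on. The length of the period also differs between patients by up to four weeks.

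There is no control arm, so the before-after contrast is the only evidence on the crofelemer half of objective 4. With just two forms per patient, no later analysis can separate the pre-dose part from the on-treatment part. The pilot is meant to inform a possible randomized trial, and a change labelled as four weeks that really covers two to three times as long would mislead its planners.

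**Working it through.** **Which visit is meant.** Four features of the text point to visit 1:

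- *Initial* ordinarily means first, and the first of the four clinic visits is the screening assessment.
- The form is an item in the Phase 1 list, which is estimated to take 4 to 8 weeks to complete.
- When the protocol means visit 2 it can say so. For the diary it writes "Participants will be provided with the Daily Symptom Diary on their second visit, prior to treatment initiation". Item 21 does not use that wording.
- The description of visit 2 includes no SF-36.

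**Inputs.** Visit 1 is 4 to 8 weeks (28 to 56 days) before treatment starts. Treatment starts on Day 1 (visit 2). The final visit is on Day 29, or the first business day after treatment ends.

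**The plan's own figure.** Day 29 − Day 1 = 28 days = 4 weeks. The stated interval is therefore reproduced exactly if the baseline is taken at visit 2.

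**Visit 1 reading.** Interval = pre-dose days + 28.

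| Screening length | Interval between forms | Share before first dose |
|---|---|---|
| 4 weeks | 28 + 28 = 56 days (8 weeks) | 28/56 = 50% |
| 8 weeks | 56 + 28 = 84 days (12 weeks) | 56/84 = 67% |

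This is 56/28 = 2 to 84/28 = 3 times the interval that the outcome names.

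**Later final visit.** Assume that the final visit moves by at most 2 days because of a weekend, with no holiday, so that it falls on Day 31:

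- Visit 1 reading: 28 + 30 = 58 days to 56 + 30 = 86 days, with 28/58 = 48% and 56/86 = 65% before the first dose. Taken together with the Day 29 case, the range is 56 to 86 days and 48% to 67%.
- Visit 2 reading: 31 − 1 = 30 days, so 28 to 30 days overall, none of it before the first dose.

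The shift does not alter the conclusion under either reading.

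**The case against.** The strongest reply is that the protocol should be read as a whole. It states a four-week interval in two places, and a visit 2 baseline satisfies both. Some of its labels favour that reading. The attachment list names form 5a as the pre-treatment survey, and the screening section calls visit 2 the pre-treatment clinic visit. Visit 1 is labelled a pre-screening assessment, not an initial visit. Being in the Phase 1 list does not fix the form at the start of screening either, because the order of those investigations is tailored to each patient. Figure 3 (the study schematic) and Attachments 5a and 5b are not shown, and any of them might name the visit. Finally, the outcome is descriptive, concerns about 25 patients, and could not be attributed to crofelemer even with a perfect baseline.

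Much of this stands. The visit 2 reading is possible, the visit 1 reading remains an inference, and the practical stakes are modest. But the reply does not remove the problem. If visit 2 was intended, item 21 still fails to name it and T0 is still not tied to a visit in the visible text. Staff who follow the more literal wording would collect the form 4 to 8 weeks too early for the stated outcome. A descriptive change still needs a correctly labelled interval, and the lack of a control is no reason to add untreated time to it.

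**Conclusion.** The concern holds as a change that should be made, with medium confidence about which visit was intended. On the natural reading, the SF-36 change runs from screening to Day 29, nominally 56 to 84 days, with half to two thirds of it before any crofelemer. This conflicts with the four-week outcome and with the crofelemer half of secondary objective 4.

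The conclusion rests on reading the initial visit as visit 1 and on the protocol's own estimate of 4 to 8 weeks for screening. The documents give no data on how SF-36 scores move before dosing, so no bias in a given direction is claimed. The primary outcome is unaffected, as is the half of objective 4 that relates diarrhea to HRQOL. A visit 1 form suits that half well.

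**What to change.** Define T0 as Day 1 (visit 2) before the first dose. Have the roughly 25 treatment-phase patients complete the SF-36 then, and report the change as Day 29 minus Day 1. If visit 2 was always intended, one sentence in item 21 naming it is enough. The screening form may be kept to describe HRQOL in all evaluated patients.

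If Day 1 forms were not collected, report the actual interval in days (median and range) and label the change as screening to Day 29, not as T+4 weeks. In either case, state that without a control arm the change cannot be attributed to crofelemer alone.

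**Cost.** No extra visit is needed.

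- *Keeping the screening form:* one more 36-item form per treated patient. Assuming that every evaluated patient completes a baseline form, the current plan needs at most 100 + 25 = 125 forms. Adding 25 makes 150 (25/125 = 20% more).
- *Moving the single baseline form to visit 2:* no added forms, but no HRQOL data for the up to 100 − 25 = 75 patients who are evaluated and not treated.
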